### **Primary Efficacy Analyses**

Efficacy analysis will be conducted the Per-Protocol Population without borrowing from historical data. A sensitivity analysis will be performed by incorporating historical data. The level of borrowing used in the safety analysis will be considered. Further sensitivity analyses on the Safety population may also be considered if the observed subject dropout rate exceeds 15%.

#### **CLUE Vision**

CLUE vision scores will be analyzed using a multivariate Bayesian normal random effects model. The model will include baseline clue score, age, add power, gender and strata (Hyperopes and Myopes) as fixed effects. Site will be included as a random effect. An unstructured (UN) covariance structure will be used to model the residual errors from measurements within the same subject across timepoints. Heterogeneous residuals covariance structures (R-side) across strata will be considered when appropriate.

The Model:

Let  $y_{ijk} = (y_{1ijk}, y_{2ijk})^T$  denote the CLUE vision scores for the  $K^{th}$  subject at the  $J^{th}$  site, in  $i^{th}$  stratum (Hyperope or Myope) at the 3-Day and 2-Week Follow-up evaluations. The likelihood for  $y_{ijk}$  is constructed as follows:

$$y_{ijk} \sim N(\mu_{ijk}, \Sigma)$$

$\mu_{ijk} = (\mu_{1ijk}, \mu_{2ijk})^T$  and  $\Sigma$  is a 2X2 variance-covariance matrix. Here,

$$\begin{aligned}\mu_{1ijk} &= \pi_1 + \mu_0 + \beta_1 Baseline_k + \beta_2 age_k + \beta_3 stratum_k + \beta_4 Gender_k + \beta_5 ADD_k + \gamma_j \\ \mu_{2ijk} &= \pi_2 + \mu_0 + \beta_1 Baseline_k + \beta_2 age_k + \beta_3 stratum_k + \beta_4 Gender_k + \beta_5 ADD_k + \gamma_j\end{aligned}$$

In this model  $\pi_1, \pi_2$ , represent the effect of time point with the constraint  $\pi_1 + \pi_2 = 0$ . In this model, we define  $stratum_k = 0$  for the Myope Strata and  $stratum_k = 1$  for the Hyperope Strata. So  $\beta_3$  stands for the difference between the Hyperope and Myope Strata with respect to CLUE vision; A positive  $\beta_3$  indicates the Hyperopes performed better than the Myopes.

We assume random site effects are independent and identically distributed (i.i.d) as  $\gamma_j \sim N(0, \sigma_{site}^2)$  for site for  $j=1, 2, 3, 4, 5, \dots, 11$  (site) . For the  $\beta$  coefficients, independent non-informative

**CR-6400**, Statistical Analysis Plan Version 1.0

priors  $N(0, 1000)$  will be used. For the variance of random effect of  $\sigma_{site}^2$  an independent non-informative conjugate prior, inverse-gamma(0.001, 0.001) will be used. For  $\Sigma$ , non-informative conjugate priors inverse-Wishart(2,S) will be used where S is a 2X2 variance-covariance matrix of  $y_{ijk}$ . The Metropolis sampler algorithm as implemented in the SAS/STAT MCMC 15.1 procedure will be used to estimate the posterior distribution of the unknown parameters. Inferences will be made based on the 95% posterior credible intervals for relevant parameters.

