- Unacceptable Len Fit: The Null hypothesis will be rejected if the upper bound of the 2-sided 95% credible interval of the posterior estimate of the proportion of eyes with unacceptable lens fitting is below 5%.

If no SLF findings of Grade 3 or higher or unacceptable lens fit is observed, alternative analysis methods will be considered. More details will be provided in the statistical analysis plan.

Primary Efficacy Analyses:

Efficacy analysis will be conducted the Intent-to-Treat Population (ITT) without borrowing from historical data. A sensitivity analysis will be performed by incorporating historical historical data. The level of borrowing used in the safety analysis will be considered. Further sensitivity analyses on the Per-Protocol Population will also be considered.

CLUE Vision

CLUE vision scores will be analyzed using a Bayesian normal random effects model for repeated measures. The model will include baseline clue score, age, add power, gender, timepoint (3-day and 2-week follow-up evaluations) and strata (Hyperopes and Myopes) and the interaction between timepoint and strata as fixed effects. Site will be included as a random effect. An unstructured (UN) covariance structure will be used to model the residual errors from measurements within the same subject across timepoints. Heterogeneous residuals covariance structures (R-side) across strata will be considered when appropriate. Non-informative priors will be used for the unknown parameter. For the β coefficients, independent non-informative priors $N(0, 1000)$ will be used. For the variance of random effect σ_{site}^2 an independent non-informative conjugate prior inverse-gamma(0.001, 0.001) will be used. For the residual covariance structure an inverse-Wishart distribution will be used. Inferences will be carried out using the 95% posterior credible intervals for relevant parameters.

Hypothesis testing for CLUE Vision Scores endpoints will be conducted separately for each stratum:

- Hyperopes: The Null hypothesis will be rejected if the lower bound of the 2-sided 95% credible interval of the clue vision posterior mean estimate is above 32.
- Myopes: The Null hypothesis will be rejected if the lower bound of the 2-sided 95% credible interval of the clue vision posterior mean estimate is above 40.

Visual Acuity

Binocular high luminance, high contrast (HLHC) visual acuity (logMAR) at the 2-week follow-up evaluation will be analyzed using a Bayesian normal random-effects model for

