Clinical Study Protocol

Johnson & Johnson Vision Care, Inc.

repeated measures. The model will include strata (Hyperope and Myope), add power, age, gender, position (40cm, 64cm and 3m) and the interaction between strata and position as fixed effects. Site and will be included as a random effect. An unstructured (UN) covariance structure will be used to model the residual errors from measurements within the same subject across different positions. Heterogeneous residuals covariance structures (R-side) across position will be considered when appropriate. Non-informative priors will be used for the unknown parameter. For the β coefficients, independent non-informative priors $N(0, 1000)$ will be used. For the variance of random effect σ_{site}^2 an independent non-informative conjugate prior inverse-gamma(0.001, 0.001) will be used. For the residual covariance structure an inverse-Wishart distribution will be used. Inferences will be carried out using the 95% posterior credible intervals for relevant parameters.

Hypothesis testing for visual acuity (logMAR) endpoints will be conducted separately for each position:

- Distance: The Null hypothesis will be rejected if the upper bound of the 2-sided 95% credible interval the binocular HLHC VA posterior mean estimate is lower than +0.10 logMAR.
- Intermediate: The Null hypothesis will be rejected if the upper bound of the 2-sided 95% credible interval the binocular HLHC VA posterior mean estimate is lower than +0.17 logMAR.
- Near: The Null hypothesis will be rejected if the upper bound of the 2-sided 95% credible interval the binocular HLHC VA posterior mean estimate is lower than +0.17 logMAR.

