## 1. INTRODUCTION

This statistical analysis plan (SAP) describes the analyses and data presentations for protocol CR-6400 Version 4.0.

This document will serve as the final guidance for all the statistical analysis for this study and will supersede the Statistical Method section in the protocol if there are any discrepancies. Any deviation from the analysis plan will be documented as such in the clinical study report.

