## 14.2. Statistical Analysis Code

### 14.2.1. Primary Analysis

#### CLUE Vision

```
PROC MCMC DATA =ads NTHREADS =12 SEED =18965237 NBI =15000 NMC
=100000 THIN=20 DIAG = ALL OUTPOST = simout DIC PLOTS(SMOOTH FRINGE) =
ALL MCHISTORY = BRIEF PROPCOV = QUANEW STATS = ALL STATS(ALPHA =
(0.05) PERCENTAGE = (2.5 50 97.5)) plots(smooth)=ALL MONITOR=(_parms_
Hyperopes_3day Myopes_3day Hyperopes_2wk Myopes_2wk);
```

```
ARRAY aval[2] FU1 FU2;
ARRAY mu[2] mu1 mu2;
ARRAY sigma[2,2];
ARRAY S[2,2] ( 1 0
0 1 );
```

```
PARMS p1 0.5 p2 0.1 beta0-beta5 ;
```

```
PARMS sigma { 1 0
0 1 };
PARMS sigma_site;
```

```
PRIOR beta: ~ NORMAL(0, var = 1000);
```

```
prior p: ~ NORMAL(0, var=1000);
```

```
PRIOR sigma ~ IWISH(2, S);
```

```
PRIOR sigma_site ~ IGAMMA(shape = 0.01, scale = 0.01);
```

```
RANDOM gamma_site ~ NORMAL(0, VAR = sigma_site) SUBJECT = siteid;
```

```
mu1 = p1 + beta0 + beta1*stratan + beta2*Base + beta3*age + beta4*sexn + beta5*addpwr +
Gamma_site;
```

```
mu2 = p1 - p2 + beta0 + beta1*stratan + beta2*Base + beta3*age + beta4*sexn + beta5*addpwr +
Gamma_site;
```

```
MODEL aval ~ MVN(mu, sigma);
```

```
BEGINNODATA;
```

```
Hyperopes 2wk = p1 + beta0 + beta1 + 0.5*beta4;
Myopes 2wk = p1 + beta0 + 0.5*beta4;
Hyperopes_3Day = p1 - p2 + beta0 + beta1 + 0.5*beta4;
Myopes_3Day = p1 - p2 + beta0 + 0.5*beta4;
```

```
ENDNODATA;
```

```
RUN;
```

Where,

CR-6400, Statistical Analysis Plan Version 1.0

Ads = Analysis dataset for CLUE Vision Scores  
 Stratan=numerical representation of strata, where Hyperopes=1 and Myopes=0  
 Base= Baseline CLUE Vision Score  
 Age= Age of subject at time of consent  
 Sexn=numerical representation of sex, where Female=1 and Male=0;  
 Addpwr=Add power of subject at baseline  
 Siteid=Site Identifier

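### The SAP's CLUE model omits the protocol's timepoint-by-strata interaction, which can bias the two stratum-specific 2-week means if hyperopes and myopes change differently

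*SAP*

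**What the plan says.** Protocol section 14.5 gives the CLUE model these terms, among others: "timepoint (3-day and 2-week follow-up evaluations) and strata (Hyperopes and Myopes) and the interaction between timepoint and strata as fixed effects".

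The SAP differs in three places:

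- **Text (section 11.1, CLUE Vision):** "The model will include baseline clue score, age, add power, gender and strata (Hyperopes and Myopes) as fixed effects". No interaction is listed.
- **Equations (same section):** π1 and π2 "represent the effect of time point with the constraint" that they sum to zero. Neither carries a stratum index, and a single stratum coefficient (β3) serves both visits.
- **Code (section 14.2.1):** "mu1 = p1 + beta0 + beta1*stratan + beta2*Base + beta3*age + beta4*sexn + beta5*addpwr" for the first follow-up and "mu2 = p1 - p2 + beta0 + beta1*stratan + beta2*Base + beta3*age + beta4*sexn + beta5*addpwr" for the second, each followed by the site effect. The stratum term is the same in both lines, so the difference between visits is `p2` in either stratum.

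The SAP lets the residual covariance differ by stratum, but that does not free the means. It gives no reason for leaving the interaction out. Its introduction says that it "will supersede the Statistical Method section in the protocol if there are any discrepancies", so the additive model is the one that will be run.

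Hypotheses 1 and 2 (SAP section 5.1) concern the 2-week mean within each stratum. Section 11.1 tests them separately, against 40 for myopes and 32 for hyperopes.

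**The concern.** An additive model estimates one time course from both strata together. Each stratum's 2-week mean then draws on the other stratum's change as well as on its own 2-week scores. That gains precision if the changes are equal. It introduces bias if they are not.

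The visit sequence makes unequal changes possible. In Protocol section 7.2, Visit 2, the CLUE questionnaire is completed at step 2.4. The decision on optimization comes at step 2.9, and a new pair is dispensed at step 2.14. The 3-day score therefore describes the lenses before optimization, and the 2-week score describes the final pair. If one stratum is modified more often or to better effect, its change will differ from the other's.

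At stake are two co-primary tests. An upward bias in a stratum whose true mean sits at its threshold raises the chance of a false pass; the other stratum is penalised by the same amount.

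**Working it through.** **Inputs from the documents.** 30 completers per stratum (SAP 3.3). Historical 2-week CLUE means and SDs: hyperopes 47.71 and 17.514, myopes 56.46 and 19.227 (SAP 8.4, Table 5). Thresholds 32 and 40. Stated power 99% for each (SAP Table 8).

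**Inputs that are assumptions.** The 3-day SD, the within-subject correlation and the between-stratum difference in change. The documents give none of them.

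**1. The plan's own power.** One-sample t test, n = 30, upper tail 0.025:

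- Hyperopes: (47.71 − 32)/17.514 × √30 = 4.91, power 0.997.
- Myopes: (56.46 − 40)/19.227 × √30 = 4.69, power 0.995.

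The stated 99% is reproduced. The planned margins are 15.71 and 16.46 points.

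**2. Size of the bias.** Let d be the hyperope change minus the myope change. Let S11, S22 and S12 be the 3-day variance, the 2-week variance and their covariance. The additive model forces the estimated d to zero. The constrained estimate of a stratum's 2-week mean is its unconstrained estimate less Cov/Var times the estimated d. For hyperopes Cov = (S22 − S12)/n and Var = 2(S11 + S22 − 2·S12)/n. The bias is therefore −f·d for hyperopes and +f·d for myopes, with

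f = (S22 − S12) / [2(S11 + S22 − 2·S12)].

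With correlation 0.6:

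| SD 3-day | SD 2-week | S12 | f | Bias if d is 8 points |
|---|---|---|---|---|
| 18 | 18 | 194.4 | 129.6/518.4 = 0.25 | 2.0 |
| 16 | 20 | 192 | 208/544 = 0.38 | 3.1 |
| 20 | 16 | 192 | 64/544 = 0.12 | 0.9 |

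The bias is zero if d = 0, and also if S12 equals S22.

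**3. Precision cost of keeping the term.** SD 18, correlation 0.6, n = 30:

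- With the interaction: 18/√30 = 3.29.
- Without it: √[(324 − 129.6²/518.4)/30] = √(291.6/30) = 3.12.
- Ratio: 3.29/3.12 = 1.05.

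**4. Error when a true mean sits on its threshold.** Take SD 18.4 at both visits (about midway between the two historical SDs) and correlation 0.6. The additive SE is 3.19 and f = 0.25. With the bias in the favourable direction, the one-sided error is 1 − Φ(1.96 − bias/SE):

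- d of 0: 2.5%.
- d of 5: bias 1.25, error 5.9%.
- d of 10: bias 2.5, error 12.0%.

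A simulation of 3000 trials per setting, with the hyperope mean at 32, gave 2.6%, 6.7% and 13.1% for the additive model. With the interaction it gave 2.6%, 3.0% and 3.3%. This was a likelihood fit without covariates or site effect, so it stands in for the planned MCMC analysis and does not replicate it.

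**5. Effect at the planning means.** Same assumptions, adverse d of 10:

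- Hyperopes: (15.71 − 2.5)/3.19 − 1.96 = 2.18, power 0.986.
- Myopes: (16.46 − 2.5)/3.19 − 1.96 = 2.42, power 0.992.

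**The case against.** The best case for the SAP is that nothing in the documents shows the two changes to differ. If they are equal, the additive model is unbiased and slightly more precise, and with 30 subjects per stratum a simpler model is defensible. Protocol 14.1 leaves detail to the SAP, and 14.10 promises that changes will be justified in the study report. Optimization is open to both strata, and no passage says it acts differently in them. All of this stands. It means that bias is possible, not established. It does not explain why a prespecified term was dropped.

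Three stronger readings are tempting and not supported.

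- **The historical gap shows that the strata change differently.** The 47.71 against 56.46 in SAP Table 5 is a difference in level at 2 weeks. The stratum coefficient already models it, and it says nothing about change from day 3.
- **The bias threatens the trial's conclusion.** At the planned margins it does not, as step 5 shows. All seven co-primaries must also be met, so a shift that helps one stratum and hurts the other gives no clear overall advantage. A false overall success would need a true mean close to 32 or 40, a sizeable difference in change in the favourable direction, and passes on every other test.
- **The acuity tests suffer in the same way.** The protocol's acuity model does list "position (40cm, 64cm and 3m) and the interaction between strata and position as fixed effects", and the SAP omits that interaction too. But hypotheses 3 to 5 concern position means pooled over strata, and the SAP code gives each stratum a weight of one half. With 30/30 completers, leaving the term out causes essentially no bias.

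**Conclusion.** The discrepancy is certain: protocol and SAP differ, the SAP governs, and its text, equations and code all impose a common 3-day to 2-week change. The consequence is conditional. If the true changes differ, the two 2-week means can be biased in opposite directions by 0.12 to 0.38 of that difference, with correlation 0.6 and the SDs tabulated. An assumed 8-point difference then gives about 1 to 3 points; equal changes give none. The point is minor at the planned margins and matters mainly if a true mean falls near its threshold. It is worth correcting because the sponsor itself prespecified the term and restoring it is cheap.

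**What to change.** Restore one timepoint-by-stratum coefficient in the SAP text, in the two mean equations and in `mu1`/`mu2`, and carry it into the stratum-specific output lines. With the existing 0/1 stratum coding it can sit in the 2-week mean only, multiplied by `stratan`; the hyperope 2-week output line then gains it and the myope line does not.

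Check the visit labels first. The output lines labelled 2wk use `p1`, which belongs to the `mu1`/FU1 expression. Those labelled 3Day use `p1 - p2`, which belongs to `mu2`/FU2. SAP 11.1 orders the scores as 3-day then 2-week; if FU1 and FU2 follow that order, the labels are reversed and a literal edit would attach the new coefficient to the wrong visit.

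If the sponsor prefers the additive model, the SAP should say why and report the interaction model as a sensitivity analysis.

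The cost is one coefficient and about 5% in standard error under the assumptions of step 3. No change to the acuity model is requested on this ground.

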### **Hypothesis Testing**

Hypothesis testing for CLUE Vision Scores endpoints will be conducted separately for each stratum (Hyperope and Myope):

The null and alternative hypotheses for CLUE vision for statistical superiority of the Hyperope stratum are as follows:

$$H_0: \mu_{Hyperope} \leq 32$$

$$H_A: \mu_{Hyperope} > 32$$

The null hypothesis will be rejected if the lower bound of the 2-sided 95% credible interval of the clue vision posterior mean estimate for the Hyperope stratum is above 32. i.e.,  $P(\mu_{Hyperope} > 32) \geq 0.975$ .

The null and alternative hypotheses for CLUE vision for statistical superiority of the Myopes stratum are as follows:

$$H_0: \mu_{Myope} \leq 40$$

$$H_A: \mu_{Myope} > 40$$

The null hypothesis will be rejected if the lower bound of the 2-sided 95% credible interval of the clue vision posterior mean estimate for the Myope stratum is above 40. i.e.,  $P(\mu_{Myope} > 40) \geq 0.975$ .

### **Binocular Visual Performance**

Binocular high luminance, high contrast (HLHC) visual performance (logMAR) at the 2-week follow-up evaluation will be analyzed using a Bayesian normal random-effects model for repeated measures. The model will include strata (Hyperope and Myope), add power, age, gender as fixed effects. Site and will be included as a random effect. An unstructured (UN) covariance structure will be used to model the residual errors from measurements within the same subject across different positions. Heterogeneous residuals covariance structures (R-side) across position will be considered when appropriate.

Let  $y_{ijkl}$  denote the visual performance for the study lens for the  $j^{th}$  subject in the  $k^{th}$  strata (Hyperope or Myope), at the  $l^{th}$ site for the  $i^{th}$ position.

The Model:

$$y_{ijkl} = \mu_0 + \beta_1 age_i + \beta_2 addpwr_j + \beta_3 dist\_yn_i + \beta_4 inter\_yn_i + \beta_5 Female_j + \beta_6 Strata_k + \delta_l + \varepsilon_{ijkl}$$

- $\mu_0$ : overall intercept
- $addpwr_i$  : ADD Power
- $dist\_yn_k$  : Distance vs. Intermediate and Near
- $inter\_yn_k$ : Intermediate vs. Distance and Near
- $Female_i$  : Female indicator; Female=1 if sex='Female' and 0 otherwise
- $Strata_j$  : Strata indicator; Strata=1 if strata='Hyperope' and 0 otherwise
- $\delta_l$  : effect of the  $l^{th}$  clinical site, a random effect
- $\varepsilon_{jkl}$ : random error associated with the  $i^{th}$  position for the  $j^{th}$  subject in the  $k^{th}$  strata at the  $l^{th}$  investigational site

Here we assume  $\delta_j$  and  $\varepsilon_{jkl}$  are independent where

- $\delta_j \sim N(0, \sigma_{site}^2)$  ;
- $\begin{bmatrix} \varepsilon_{1jkl} \\ \varepsilon_{2jkl} \\ \varepsilon_{3jkl} \end{bmatrix} \sim N \left( \begin{bmatrix} 0 \\ 0 \\ 0 \end{bmatrix}, \begin{bmatrix} \sigma_{11}^2 & \sigma_{12} & \sigma_{13} \\ \sigma_{21} & \sigma_{22}^2 & \sigma_{23} \\ \sigma_{31} & \sigma_{32} & \sigma_{33}^2 \end{bmatrix} \right)$

We assume random site effects are independent and identically distributed (i.i.d) as  $\gamma_j \sim N(0, \sigma_{site}^2)$  for site for  $j=1, 2, 3, 4, 5, \dots, 11$  (site) . For the  $\beta$  coefficients, independent non-informative priors  $N(0, 1000)$  will be used. For the variance of random effect of  $\sigma_{site}^2$  an independent non-informative conjugate prior, inverse-gamma(0.001, 0.001) will be used. For the variance of  $y_{ijkl}$  an independent non-informative conjugate prior, inverse-gamma(0.001, 0.001) will be also used. The Metropolis sampler algorithm as implemented in the SAS/STAT MCMC 15.1 procedure will be used to estimate the posterior distribution of the unknown parameters. Inferences will be made based on the 95% posterior credible intervals for relevant parameters.

### **Hypothesis Testing**

The null and alternative hypothesis for binocular distance HLHC visual performance to test for superiority of the Test lens relative to the pre-defined threshold of 0 logMAR is as follows:

$$H_0: \mu_{Test} \geq 0.10 \text{ logMAR}$$

$$H_A: \mu_{Test} < 0.10 \text{ logMAR}$$

Superiority will be declared if the upper limit of the 95% CrI is below 0.10 logMAR. i.e.  $P(\mu_{Test} < 0.10) \geq 0.975$ .

The null and alternative hypothesis for binocular near HLHC visual performance to test for superiority of the Test lens relative to the pre-defined threshold of 0.17 logMAR is as follows:

$$H_0: \mu_{Test} \geq 0.17 \text{ logMAR}$$

$$H_A: \mu_{Test} < 0.17 \text{ logMAR}$$

Superiority will be declared if the upper limit of the 95% CrI is below 0.17 logMAR. i.e.  $P(\mu_{Test} < 0.17) \geq 0.975$ .

The null and alternative hypothesis for binocular distance HLHC visual performance to test for superiority of the Test lens relative to the pre-defined threshold of 0.17 logMAR is as follows:

$$H_0: \mu_{Test} \geq 0.17 \text{ logMAR}$$

$$H_A: \mu_{Test} < 0.17 \text{ logMAR}$$

Superiority will be declared if the upper limit of the 95% CrI is below 0.17 logMAR. i.e.  $P(\mu_{Test} < 0.17) \geq 0.975$ .

## 11.2. Secondary Analysis

### Proportion of Subjects with Optimal Lens Pair

The number of lenses used for each subject will be calculated as the original pair (2) plus all the required modifications to reach the optimal pair. In this study the minimum number of lenses per subject used would be 2 where the max would be 6. The data will be dichotomized as 1 if the subject was able to achieve optimal lens pair in 4 lenses or less and 0 otherwise. The binary response will be analyzed using Bayesian logistic regression random-effects model to estimate the proportion of eyes that reached optimal lens pair in 4 lenses or less. The regression model will include strata (Hyperope and Myope), add power, age, gender, event (fitting, optimization, 2-week follow-up) and the interaction between strata by event. Site will be included in the model as a random effect. Non-informative priors will be used for the unknown parameter. For the  $\beta$  coefficients, independent non-informative priors  $N(0, 1000)$  will be used. For the variance of random effects of  $\sigma_{\text{site}}^2$  non-informative conjugate prior, inverse-gamma (0.001, 0.001) will be used. Inferences will be made based on the posterior credible interval for the relevant parameters.

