14.6. Secondary Analysis

The secondary Hypothesis will be conducted on the Intent-to-Treat without borrowing historical data.

Proportion of Subjects with Optimal Lens Pair

The number of lenses used for each subject will be calculated as the original pair (2) plus all the required modifications to reach the optimal pair. In this study the minimum number of lenses per subject used would be 2 where the max would be 6. The data will be dichotomized as 1 if the subject was able to achieve optimal lens pair in 4 lenses or less and 0 otherwise. The binary response will be analyzed using Bayesian logistic regression random-effects model to estimate the proportion of eyes that reached optimal lens pair in 4 lenses or less. The regression model will include strata (Hyperope and Myope), add power, age, gender, event (fitting, optimization, 2-week follow-up) and the interaction between strata by event. Site will be included in the model as a random effect. Non-informative priors will be used for the unknown parameter. For the β coefficients, independent non-informative priors $N(0, 1000)$ will be used. For the variance of random effects of σ_{site}^2 non-informative conjugate prior, inverse-gamma

Clinical Study Protocol

Johnson & Johnson Vision Care, Inc.

(0.001, 0.001) will be used. Inferences will be made based on the posterior credible interval for the relevant parameters.

The null hypothesis will be rejected if the lower bound of the 2-sided 95% credible interval the proportion of subjects is above 90%.

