### 3.3. Targeted Study Population and Sample Size

Approximately 80 subjects will be enrolled to ensure that 60 subjects will complete the study (30 myopes and 30 hyperopes). Enrolled subjects will be habitual wearers of soft contact lenses. All subjects will be at least 40 years of age and not older than 70 years of age at the time of enrolment. Eligible presbyopes will be those that wear an a presbyopic contact lens correction (e.g., reading spectacles over contact lenses, multifocal or monovision contact lenses, etc.) or if not respond positively to at least one symptom on the “Presbyopic Symptoms Questionnaire” (CR-6400 Protocol Version 4.0, Appendix E).

Table 2: Planned Enrollment Strategy by Strata and Site

	Myopes	Hyperopes	Total
Enrolled	40	40	80
Randomized	30	30	60
Number of enrolled per site (min-max) Target	2-6	2-6	

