## 8.5. Statistical Significance Level

All planned analysis for this study will be conducted with an overall type I error rate of 5%.

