#### **The Model:**

Let  $Y_1$  and  $Y_2$  denote the binary outcomes for the left and right eyes, respectively, when wearing the test lens. Considering the correlation,  $\rho$ , between  $Y_1$  and  $Y_2$ , the distribution of the CR-6400, Statistical Analysis Plan Version 1.0

sum  $Y = Y_1 + Y_2$  is obtained by the mixture of two variables. One of them follow a binomial distribution  $\text{Bin}(2, p)$  with mixing probability  $(1-\rho)$  and the other one follows a modified Bernoulli distribution  $\text{MBern}(p)$ , taking value 0 and 2 rather than conventional 0 and 1, with mixing probability  $p$ :

$$P(Y = y | p, \rho) = (1 - \rho)\text{Bin}(2, p)I_{A1} + \rho\text{MBern}(p)I_{A2};$$

where  $I_{A1} = \{0, 1, 2\}$  and  $I_{A2} = \{0, 2\}$

To overcome the complexity of the mixture likelihood a latent variable  $Z_i$ ,  $i = 1, 2$  is introduced in the model to indicate in which component of the model the observation  $y_i$ ,  $i=1, 2$ , belongs to, that is,

$$z_i = \begin{cases} 1, & \text{if the observation belong to the } \text{MBern}(p), \\ 0, & \text{if the observation belong to the } \text{Bin}(2, p) \end{cases}$$

The joint distribution of the augmented data  $(Y_i, Z_i)$ ,  $i=1, 2$ , is given by

$$P(Y = y_i, Z = z_i | p, \rho) = \rho^{z_i} p^{y_i z_i / 2} (1 - p)^{(2 - y_i) z_i / 2} (1 - \rho)^{1 - z_i} \binom{2}{y_i} p^{y_i (1 - z_i)} (1 - p)^{(2 - y_i) (1 - z_i)}$$

The posterior distribution of  $(p, \rho)$  given  $(y, z)$ ,  $(y_0, z_0)$  and  $a_0$  is

$$P(p, \rho | | y, z, y_0, z_0, a_0) = P(y, z | p, \rho) P(y_0, z_0 | p, \rho)^{a_0} \pi_0(p, \rho)$$

where,  $\pi_0$  is joint prior distribution of  $(p, \rho)$ . Here we assume  $p$  and  $\rho$  to be independent with a prior beta  $(\alpha, \beta)$  for  $p$  and uniform  $(0,1)$  for  $\rho$ . Hence the joint distribution of  $(p, \rho)$  is given by  $\pi_0(p, \rho | \alpha, \beta) \propto p^{\alpha-1} (1-p)^{\beta-1}$ . The Metropolis sampler algorithm as implemented in the SAS/STAT MCMC Procedure will be used to estimate the posterior distributions of the parameters  $(p, \rho)$ . Inferences will be made based on a posterior credible interval for the relevant parameters.

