### Hypothesis Testing

With respect to the proportion of subjects that have achieved optimal fitting in 4 lenses or less, the null and alternative hypothesis for superiority is as follows:

$$H_0: p_T \leq 0.90$$

$$H_A: p_T > 0.90$$

Where,  $p_T$  represents the proportion of subjects that have achieved optimal fitting in 4 lenses or less. Success for will be declared if the lower bound of the 2-sided 95% credible interval of the proportion is greater than 0.90; i.e.  $P(p_T > 0.90) \geq .975$ .

If not enough events occur during the duration of this study the model presented for the safety population.

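### The secondary lens-count test (SAP 11.2) uses a diffuse-prior logistic model that does not hold its implied 2.5% error rate, and its fallback is a two-eye model for a one-per-subject outcome

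*SAP*

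**What the plan says.** SAP 11.2 defines the outcome per subject: "The data will be dichotomized as 1 if the subject was able to achieve optimal lens pair in 4 lenses or less". The next sentence moves to eyes: "The binary response will be analyzed using Bayesian logistic regression random-effects model to estimate the proportion of eyes that reached optimal lens pair". Protocol 14.6 has the same shift ("The binary response will be analyzed using Bayesian logistic regression random-effects model to estimate the proportion of eyes"). The hypotheses in SAP 11.2 are about subjects.

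The model contains strata, ADD power, age, gender, a three-level event term, strata by event, and a random site effect. Coefficients have N(0,1000) priors; the code in SAP 14.2.1 for the other models treats 1000 as a variance.

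The decision rule is: "Success for will be declared if the lower bound of the 2-sided 95% credible interval of the proportion is greater than 0.90", also written as a posterior probability of at least 0.975. SAP 8.5 sets the level: "All planned analysis for this study will be conducted with an overall type I error rate of 5"%.

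For sparse data the SAP offers only this: "If not enough events occur during the duration of this study the model presented for the safety population". The sentence has no verb and gives no threshold. The model it appears to mean, in SAP 11.1, describes the sum of left- and right-eye outcomes. One component of that model is a modified Bernoulli "taking value 0 and 2 rather than conventional 0 and 1".

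There is no code, power or error rate for this test. The SAP does not say at which covariate values the proportion is read, whether covariates are centred, or how a three-level event enters when each subject contributes one outcome.

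**The concern.** To show a proportion above 0.90 with about 60 subjects, only a handful of failures can be tolerated. A logistic model with five or more coefficients is then fitted to very few failures, and covariates can separate them completely or nearly so. Under priors as wide as N(0,1000), slopes can become very large, most fitted probabilities move towards 1, and the lower bound reflects the prior as much as the data. Even with no covariates, a near-flat prior on the logit favours proportions close to 0 or 1.

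At stake is the error rate of the only formal secondary hypothesis: a lens whose true proportion is exactly 90% could be declared to exceed 90% far more often than intended. The fallback raises a separate question of unit, because it is built for pairs of eyes.

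**Working it through.** **Inputs from the documents.** Null value 0.90 and the 0.975 rule (SAP 11.2); overall 5%, so 2.5% in the tested tail (SAP 8.5); 60 completers from about 80 enrolled (SAP 3.3); N(0,1000) coefficients (SAP 11.2); Beta(0.5,0.5) for p and uniform(0,1) for the between-eye correlation in the safety model (SAP 14.2.1).

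**Assumed for the simulation, not in the documents.** Age about N(53,7) cut to 40–70, ADD related to age, 67% female, covariates unrelated to outcome. The 11 sites follow the index in SAP 11.1.

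**Step 1: what a 2.5% test allows at n = 60.** With failures distributed Binomial(60, 0.10), P(≤1) = 0.014, P(≤2) = 0.053 and P(≤3) = 0.137.

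| Failures | Exact lower bound | P(p > 0.90), Beta(1,1) | P(p > 0.90), Beta(0.5,0.5) |
|---|---|---|---|
| 1 | 0.911 | 0.987 | 0.994 |
| 2 | 0.885 | 0.951 | 0.971 |

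All three methods stop at one failure, an error of 1.4%.

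**Step 2: the planned prior with no covariates.** An intercept with N(0,1000) on the logit gives P(p > 0.90) = 0.985 at two failures and 0.943 at three. Two failures therefore pass, and the error is P(≤2) = 5.3%. As a check, a flat prior on the logit gives a Beta(58,2) posterior at two failures, and 1 − P(Binomial(59, 0.10) ≤ 1) = 0.985.

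**Step 3: strata, ADD, age and sex, without site or event.** Data were simulated at a true proportion of 0.90, 70 data sets for each failure count from 0 to 10. Error = sum over k of P(k failures) × share of data sets with k failures that pass. Because outcome is unrelated to covariates, the true value is 0.90 under both of the first two readings below.

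- *Averaged over subjects.* 0–2 failures always pass, and 9% pass at three: 0.053 + 0.084 × 0.09 = 0.061. Repeat runs gave 6.0–6.8%.
- *At mean covariates.* 0–3 failures always pass; then 79%, 40%, 17% and 13% pass at four to seven: 0.137 + 0.134 × 0.79 + 0.166 × 0.40 + 0.169 × 0.17 + 0.145 × 0.13 = 0.357, and about 0.362 with the small remainder. Repeat runs gave 35.2–36.3%; allowing for simulation error, about 35–40%.
- *Age and ADD set to zero, as the CLUE code does.* About 4–9%, unstable between runs.

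**Step 4: the omitted terms.** Adding the site effect gave about 10% averaged and 42% at mean covariates. Adding event terms raised the error further, but required an invented split of subjects across events.

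**Step 5: cause.** At mean covariates, with slopes per standard deviation, slope prior variances of 1000, 1 and 0.1 give errors of 36%, 15% and 5.4%. The diffuse slope priors are a main driver.

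**Step 6: the fallback.** If a failing subject is coded Y = 2 in the two-eye model, two failures pass (upper bound for the failure proportion 0.091), an error of 5.3%. No coding is given.

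**Step 7: dependence on n.** At n = 80, P(≤2) = 0.011 and P(≤3) = 0.035. The exact lower bound is 0.913 at two failures and 0.894 at three, so two are allowed (error 1.1%). Beta(1,1) gives 0.990 and 0.967, the same limit. Beta(0.5,0.5) passes three (P = 0.980), an error of 3.5%.

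**The case against.** The best defence is that the SAP is incomplete here, so any single error rate belongs to the analyst's reading of it. Much of this stands:

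- A reader might infer that the planned test can be met only with zero or one failure. The documents do not support that. It is the limit of a valid 2.5% test; the planned model passes with two or more.
- A reader might take 35–40% as the plan's error rate by assuming that the SAP's own convention is to read estimates at mean covariates. The CLUE and visual performance code in SAP 14.2.1 instead leaves age and ADD out, which sets them to zero, and puts only sex (and, for visual performance, strata) at 0.5. That code also covers primary analyses only.
- A reader might quote a much larger error for the fallback by coding a failing subject as one affected eye. No document gives that coding, and it is an unnatural one for a subject-level failure.
- SAP 5.1 tests this hypothesis only after all seven co-primaries succeed, so it cannot change whether the primary objectives are met. SAP 5.2 also words the target as at least 90%, although the formal alternative in SAP 11.2 is above 0.90.
- n = 60 is an assumption. Protocol 14.6 puts this test on the ITT set, SAP 11.2 names none, and SAP 6.4 makes per-protocol primary.

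These points limit the size that can be claimed but do not restore the error rate. None of the readings checked for the N(0,1000) model reached 2.5%. Gating limits how often the test is reached, not its error once reached.

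**Conclusion.** The concern holds as a failure to control the error rate of one gated secondary hypothesis. At n = 60 and a true proportion of 0.90, the N(0,1000) prior alone roughly doubles the implied 2.5% to about 5%. With four covariates the error is about 6–7% averaged over subjects, about 35–40% at mean covariates, and about 4–9% with age and ADD at zero. The planned site and event terms raise it further. These figures rest on the assumed covariate distributions and on outcome being unrelated to covariates, so they show a range across readings the SAP leaves open, not one error rate for the plan. The fallback does not fit the unit of the outcome, and its intended use has to be inferred from an unfinished sentence. This should be fixed, but it gives no reason to doubt the primary analyses.

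**What to change.** In SAP 11.2:

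1. Use one record per subject on a named analysis set, reconciling ITT in protocol 14.6 with per-protocol in SAP 6.4.
2. Declare success if the exact (Clopper-Pearson) two-sided 95% lower bound exceeds 0.90. If a Bayesian form is preferred, require P(p_T > 0.90) ≥ 0.975 under Beta(1,1); it gives the same limits at n = 60 (one failure, error 1.4%) and n = 80 (two failures, error 1.1%). State the limit for the final n. Beta(0.5,0.5) is not suitable, since it gives 3.5% at n = 80.
3. Keep any covariate model as descriptive only.
4. Delete the fallback sentence, and refer to subjects, not eyes, in the estimand.

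The change is to wording, with no new data. It gives up covariate adjustment, which a single-arm comparison with a fixed target does not need. Power is lower than the present rule would appear to offer: with at most one failure in 60 it is 19% at a true proportion of 0.95, 46% at 0.97, 66% at 0.98 and 88% at 0.99. The SAP should state this.
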